During the pre-surgery PK assessment and during the period starting with the initial loading dose until the end of the surgery study, subjects will receive BAX 855 from the surgery study. Any data collected during these periods will be recorded as part of the surgery study.

EDs will be counted in the subjects' primary study, ie BAX 855 EDs accumulated as part of the surgery study will also be factored into the total number of EDs in the continuation study.

For subjects transitioning back from the surgery study to this study, the investigator will determine whether the subject continues to meet the eligibility criteria using end of study data from the surgery study.

8.7.5 . Investigational Product Accountability

The investigator will ensure that the IP is stored as specified in the protocol and that the storage area is secured, with access limited to authorized study personnel. The investigator will maintain records that the IP was received, including the date received, drug identity code, date of manufacture or expiration date, amount received and

vi Subjects undergoing major surgeries who have undergone a PK determination in the current study do not require a pre-surgical PK assessment.

vii Subjects undergoing minor surgeries but do not have an IR performed within 3 months of surgery have to perform an IR.

disposition. IP must be dispensed only at the study site or other suitable location (eg, infusion center, home, as applicable per study design). Records will be maintained that includes the subject identification code (SIC), dispensation date, and amount dispensed. All remaining partially used and/or unused IP will be returned to the study site, which will then return it to the sponsor or sponsor's representative after study completion/termination, or destroyed with the permission of the sponsor in accordance with applicable laws and study site procedures. If IP is to be destroyed, the investigator will provide documentation in accordance with sponsor's specifications.

For further detail, please refer to the pharmacy and IP distribution manual for this study.

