9.3 Withdrawal and Discontinuation

Any subject may voluntarily withdraw (ie, reduce the degree of participation in the study) consent for continued participation and data collection. The reason for withdrawal will be recorded on the End of Study eCRF. Assessments to be performed at the end of study visit (including in cases of withdrawal or discontinuation) are described in Section 10.6 and Section 20.3.

Discontinuation (ie, complete withdrawal from study participation) may be due to dropout (ie, active discontinuation by subject) or loss to follow-up (ie, discontinuation by subject without notice or action). Additionally, the investigator and sponsor have the discretion to discontinue any subject from the study if, in their judgment, continued participation would pose an unacceptable risk for the subject.

Subjects also may be withdrawn from treatment or discontinued from further study participation for the following reasons:

- The subject develops a confirmed high responder inhibitory antibody to FVIII (>5 BU by Nijmegen modification of the Bethesda assay) or a low responder inhibitory antibody (≤ 5 BU but ≥ 0.6 BU) that cannot be managed by the protocol-required treatment.
- The subject experiences a severe anaphylactic reaction to BAX 855.
- The subject requires therapy with another PEGylated product (eg, PEG-Interferon).
- The subject frequently misses administration of IP (ie, misses more than 30% of planned prophylactic doses within any 3-month period).
- The subject is non-compliant with study procedures, in the opinion of the investigator.

- The subject repeatedly uses another FVIII therapy for prophylaxis (in the absence of an acceptable justification to the sponsor) or for the treatment of bleeding episodes.
- The subject requires a surgical or dental procedure and is not eligible or does not consent for the surgery study, or participates in the surgery study and then refuses to resume participation in this continuation study. If the surgery study is closed, the subject will be withdrawn from the continuation study.
- The subject experiences a life-threatening bleeding episode (eg, any gastrointestinal hemorrhage or intracranial hemorrhage).
- The subject experiences severe trauma or requires emergency surgery with FVIII replacement therapy other than BAX 855.

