#### 4.4 Per Protocol Analysis Set (PPAS)

The per protocol (PPAS) analysis set is to comprise all subjects in the FAS who had no major deviations from the protocol affecting the study results. Protocol deviations are to be obtained from the Clinical Trial Management System (CTMS).

Prior to performing any analysis as set out in this SAP, a meeting is to be held discussing the impact of any major protocol deviation on the analysis. At this meeting, the decision is to be made on whether a subject is to be excluded from the PPAS analysis set or not. The meeting is to be attended by participants from at least Biostatistics and Medical.

Below is a list of possible major deviations that may influence the study results that will be discussed at the analysis set assignment meeting:

- Subject less than 75% exposed to BAX 855 as derived in Section 6.8: Measurements of Treatment Compliance.
- Subject less than 75% compliant to planned dosing regimen.
- More than 10% of treated bleeds have no efficacy rating.
- Use of expired IP.
- Subject did not reach 100 EDs across all BAX 855 studies.
- Use of any FVIII product other than ADVATE, as determined by the medical team.

It should be noted that the above will not necessarily lead to immediate exclusion from the PPAS, but will be discussed prior to locking the database. The database is not allowed to be locked until final approval on the PPAS has been obtained.

During the course of the study, data review meetings are to be held on a regular basis. During these meetings the quality of the data including any potential protocol deviations are to be identified. All protocol deviations identified at these meetings are to be included into the CTMS upon team agreement.

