## 6.7 Extent of Exposure

The following information is to be obtained from the eCRF:

- Information on study infusions (*Study Infusions* eCRF panels).
- Treatment regimen, including planned dose (*Treatment Assignment* and *Change of Treatment Assignment* eCRF panels).
- Body weight (*Vital Signs* eCRF panels).

The following derivations based on eCRF reported results are to be performed:

- Body weight-adjusted dose (IU/kg) is to be derived as the total units infused (IU) divided by the last available body weight (kg) prior to the infusion. Refer to Section 5.4: Handling of Missing, Unused, and Spurious Data for imputation schemes to be implemented.
- Total number of infusions in this study are determined as the count of the number of infusions, regardless of date and time, the subject had. Number of infusions are to be determined overall and by reason for infusion as well as by the treatment regimen assigned to at the time of receiving the treatment.
- The number of EDs are determined as the number of unique calendar days on which a subject received any or part of any infusion. Multiple infusions on the same day are still to be considered one ED. EDs are to be determined overall as well as for each reason an infusion is given. The number of EDs will be determined for this study and across all previous BAX 855 studies the subject participated in. EDs in this study will be derived as the number of infusions on unique calendar days in this study, while EDs from previous BAX 855 studies will be obtained as reported in the eCRF. The total EDs across all BAX 855 studies will be determined as the sum of EDs in current study and EDs in previous studies.
- The observation period for efficacy (OPE) in days in the study for subjects who never transferred to the surgery study is to be determined as:

$$OPE(Days) = (Stop\ Date - Start\ Date) + 1$$
 where "Start Date" refer to the first BAX 855 infusion in the current study and "Stop Date" to the last BAX 855 infusion in the current study. For subjects on the PK-guided regimen, first BAX 855 infusion will be the first prophylactic infusion.

• The OPE in days for subjects that did transfer to the surgery study is to be determined as:

$$OPE(Days)$$

$$= (Date\ of\ Transfer\ to\ Surgery\ Study - Start\ Date) + (Stop\ Date - Return\ Date\ to\ Current\ Study) + 1$$
where "Start\ Date" and "Stop\ Date" are\ defined\ as\ above.

• The OPE in weeks is to be determined from the OPE in days as:

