#### **6.8** Measurements of Treatment Compliance

Treatment compliance is to be derived using results and derivations obtained from study exposure as described in Section 6.7: Extent of Exposure.

Treatment compliance is to be based on the following:

- Adherence to the infusion schedule; and
- Adherence to recommended prophylactic dose.

An infusion is considered to be in adherence to the infusion schedule if:

- Time since last infusion on the "twice weekly regimen" do not exceed 5 days.
- Time since last infusion on the "every 5 day regimen" do not exceed 5 days.
- Time since last infusion on the "every 7 day regimen" do not exceed 7 days.
- Time since last infusions on the "other dosing regimen" do not exceed the days specified by the investigator.

Based on the treatment regimen, time that a subject was not exposed to BAX 855 is to be determined. Time a subject was not exposed to BAX 855 is to be derived as:

- = Days since last BAX 855 infusion
- Treatment regimen allowed days

Time not exposed (days) is to be set to 0 days if the above derivation results in number of days less than 0. The total time not exposed to BAX 855 for each subject will be determined as the sum of times not exposed for each individual infusion.

The percentage of time a subject was exposed to BAX 855 is to be derived as follows:

$$\textit{Time Exposed (\%)} = \frac{\textit{OPE(Days)} - \textit{Total Time not Exposed (Days)}}{\textit{OPE(Days)}} \times 100$$

An infusion is considered to be in adherence to the recommended prophylactic dose if the actual amount infused (IU/kg) are between 90% and 110% of the planned dose (IU/kg) to be infused. Infusions with actual amount infused not recorded in the eCRF are to be excluded from the compliance calculations.

The number and percentage of infusions in adherence to the recommended prophylactic dose will be determined for each subject and treatment regimen using the overall number of infusions for that subject as denominator.

Treatment compliance are to be summarized for the SAS and PPAS and listed for the SAS. Summaries are to be presented by age category and treatment regimen at time of dose on a subject level.

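### SAP 6.7 and 6.8 treat time in surgery study 261204 inconsistently: percentage of time exposed is understated after a return, and the observation period is undefined without one

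*SAP*

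**What the plan says.** **Observation period (SAP 6.7).** There are two formulas. One is limited to subjects who stayed in 261302 throughout: "The observation period for efficacy (OPE) in days in the study for subjects who never transferred to the surgery study is to be determined as" (Stop − Start) + 1. The other covers the rest: "The OPE in days for subjects that did transfer to the surgery study is to be determined as" (Transfer − Start) + (Stop − Return) + 1. Start and Stop are the first and last BAX 855 infusions in the current study, so the second formula removes the interval between transfer and return.

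**Compliance (SAP 6.8).** For each infusion, time not exposed is the number of days since the last BAX 855 infusion minus the days the regimen allows, floored at zero. Then: "The total time not exposed to BAX 855 for each subject will be determined as the sum of times not exposed", taken over every infusion. The percentage of time exposed is (OPE − total time not exposed)/OPE. The section builds on 6.7: "Treatment compliance is to be derived using results and derivations obtained from study exposure as described in Section 6.7: Extent of Exposure". The infusion source listed there is "Information on study infusions (*Study Infusions* eCRF panels").

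**Use of the result (SAP 4.4).** "Subject less than 75% exposed to BAX 855 as derived in Section 6.8" heads the list of possible major deviations to be discussed when the per-protocol set (PPAS) is assigned.

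**What happens during the absence (Protocol 8.7.4).** During the pre-surgical PK assessment, and from the loading dose to the end of the surgery study, "subjects will receive BAX 855 from the surgery study", and the data from those periods are recorded in that study.

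**Non-return.** Protocol 9.3 lists as a ground for withdrawal a subject who "participates in the surgery study and then refuses to resume participation in this continuation study". Protocol 8.7.4 makes return conditional on being able to resume the regimen, on sponsor approval and on continued eligibility.

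**The concern.** The ratio in SAP 6.8 uses two different clocks. The denominator stops while the subject is in the surgery study; the subtracted term does not. A subject who was treated throughout, and who kept exactly to schedule in 261302, can look under-exposed because of an operation.

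The second gap lies upstream, in the OPE itself. The transferred-subject formula cannot be evaluated without a return date. The OPE is the denominator of each subject's ABR, and its logarithm is the offset in the models for spontaneous ABR, a co-primary outcome. It also feeds the yearly AE rate (SAP 8.1) and the annualized resource-use summaries (SAP 10.3 and 10.4). An undefined OPE therefore leaves bleeds and time already recorded before transfer with no stated place in the analysis. Both problems fall only on subjects who needed surgery, so they are not a random subset.

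**Working it through.** The documents give no numerical result on this point, so there is no figure to reproduce. The check applies the SAP formulas as written.

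**Part 1: time exposed after a return**

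Inputs:
- Allowed interval on the twice-weekly regimen: 5 days (SAP 6.8).
- Infusion dates: current study only (SAP 6.7 source; Protocol 8.7.4 on where surgery-period data are recorded).
- OPE: 91 to 365 days, from the planned participation of about 3 to 12 months (SAP 6.1).
- Gap: days from the last current-study infusion before transfer to the first after return. The documents give no value, so it is an assumption.

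An adherent subject's other intervals are 3 or 4 days and contribute nothing to time not exposed. Only the interval spanning the absence contributes, and it adds gap − 5. Hence:

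Time exposed = (OPE − (gap − 5))/OPE.

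This is below 75% when gap > 5 + 0.25 × OPE, and negative when gap > OPE + 5.

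| OPE (days) | Below 75% when gap exceeds | Negative when gap exceeds |
|---|---|---|
| 91 | 5 + 22.75 = 27.75 | 96 |
| 180 | 5 + 45 = 50 | 185 |
| 365 | 5 + 91.25 = 96.25 | 370 |

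Worked values for assumed gaps:
- OPE 91, gap 28: (91 − 23)/91 = 74.7%
- OPE 180, gap 28: (180 − 23)/180 = 87.2%
- OPE 180, gap 60: (180 − 55)/180 = 69.4%
- OPE 350, gap 60: (350 − 55)/350 = 84.3%

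The gap is slightly longer than the transfer-to-return absence, because it also includes the days between the last infusion and the transfer. A day-by-day schedule confirms the formula. It used alternating 3- and 4-day intervals, one transfer, and an infusion on the day of return:

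| OPE (days) | Absence (days) | Time not exposed (days) | Time exposed as written |
|---|---|---|---|
| 91 | 28 | 26 | 65/91 = 71.4% |
| 91 | 120 | 118 | −27/91 = −29.7% |
| 178 | 56 | 54 | 124/178 = 69.7% |
| 365 | 90 | 89 | 276/365 = 75.6% |
| 365 | 120 | 119 | 246/365 = 67.4% |

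In the first row the gap is 26 + 5 = 31 days for a 28-day absence. If the spanning interval is left out, every row returns 100%.

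**Part 2: OPE without a return**

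1. The transferred-subject formula contains (Stop − Return). With no return date, that term has no value.
2. The other formula is confined to subjects who never transferred, so it does not apply.
3. SAP 6.1 collects the return panel only where applicable, so a blank is expected.
4. SAP 5.4 rules out imputation apart from listed exceptions, and this date is not one of them.
5. SAP 7.1 divides bleeds by OPE for the ABR and uses log(OPE) as the offset, so neither can be computed. Nor can the percentage in SAP 6.8.
6. SAP 7.1 admits only subjects with 100 or more EDs to the ABR models. The missing offset therefore removes a non-returner from the model only if that subject had reached 100 EDs. The descriptive ABR summaries state no such restriction.

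The formula also has room for only one transfer and one return.

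**The case against.** **Another reading of the last infusion.** SAP 6.8 does not add that the last infusion must be in the current study, although the SAP adds that limit elsewhere. Protocol 8.7.4 counts surgery-study EDs toward the continuation-study total. If surgery-study infusions were merged in, the false gap would largely disappear. This has some force: the SAP nowhere says in words that the absence is untreated. But the only infusion source it names for this derivation is the current-study panel, and it describes no link to surgery-study infusions. Even on the merged reading, the OPE would exclude the period in which those infusions fall.

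**Exclusion from the PPAS.** A reader might infer that surgical subjects would be excluded automatically. The documents do not support that. SAP 4.4 says a listed deviation does not necessarily lead to exclusion, the decision is taken at a meeting before lock, and the transfer and return dates are listed. ABR is also presented on the full analysis set.

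**Loss from the ABR model.** A reader might infer that every non-returner is lost because of the OPE. Those below 100 EDs are out of the model under SAP 7.1 in any case.

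**Number affected.** The surgery study's planned enrolment of about 40 (Protocol 6.1) is tempting as a count. It is not one: that study also takes naive subjects and subjects from other BAX 855 studies, and some minor interventions can be managed without transfer.

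**Longer participation.** Protocol 8.3 allows extension beyond 100 EDs, which dilutes Part 1. At OPE 730, a 60-day gap gives (730 − 55)/730 = 92.5%, and the trigger needs a gap above 187.5 days.

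**Conclusion.** Both gaps are real and limited to subjects who transfer.

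Part 1 gives a wrong compliance percentage, possibly a negative one, and can raise a false flag for the PPAS meeting. Within planned participation, the gap that crosses 75% runs from about 28 days (OPE 91) to about 96 days (OPE 365). This assumes the twice-weekly regimen, otherwise perfect adherence, and infusion data from the current study only.

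Part 2 matters more because it reaches the ABR. For a subject who does not return, the OPE and the descriptive ABR are undefined, and so is the model offset if the subject has at least 100 EDs. The documents do not give the length of absences, the number of transfers or the number of non-returns, so the effect on the overall ABR estimate cannot be sized. The SAP should be corrected; nothing here shows that the study's conclusions would change.

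**What to change.** - **SAP 6.8:** do not compute time not exposed across a transfer-to-return interval. Restart the clock at the first infusion after return.
- **SAP 6.7:** define the OPE as the sum of the intervals spent in 261302. When there is no return, the period ends at transfer and there is no second term. Handle repeat transfers the same way, and state whether the day of transfer counts.
- **Transfer date:** define it consistently with Protocol 8.7.4. Data up to the loading dose belong to 261302, except the pre-surgical PK assessment, which is recorded in the surgery study. Taking the loading dose alone as the transfer date would therefore count some surgery-study time as OPE for subjects who have that assessment.

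The Transfer and Return panels in SAP 6.1 already hold the main dates. The cost is a few lines of SAP text and programming, with no change to study conduct.

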8.7.3 Description of Treatment

Subjects will be treated on either a fixed dose or PK-tailored prophylactic treatment regimen^{iv} until they reach at least 100 EDs (accumulated across all studies). Subjects who received on-demand treatment in the pivotal study (Study 261201) and decide to receive a PK-tailored treatment regimen in this study will first receive a fixed dose prophylactic treatment regimen (as outlined in Section 8.7.3.1) until their dose and frequency is determined and the first PK-tailored dose administered.

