8.7.3.5 Treatment of Bleeding Episodes

BAX 855 will be used for the treatment of bleeding episodes (ie, breakthrough bleeding episodes during prophylaxis), according to the guidelines outlined in [Table 3](#). These guidelines may be adjusted (ie, below $10 [\pm 5]$ IU/kg or above $60 [\pm 5]$ IU/kg) by the investigator based upon his or her clinical judgment and the severity of the bleeding episode (see [Table 3](#)).

It is critical that treatment of a bleed is initiated as soon as possible after occurrence of the bleeding episode.

When bleeding is controlled, additional infusions of BAX 855 to maintain hemostasis is permitted, if required. The infusion for maintenance of hemostasis should be administered within 24 hours of the most recent infusion. Otherwise it is considered a prophylactic infusion.

Table 3 BAX 855 Treatment Guidelines for Bleeding Episodes		
Type of Bleeding Episode	FVIII Level Required (%) Dose (IU/kg)	Frequency of Dosing
Minor Early hemarthrosis, mild muscle bleeding, or mild oral bleeding, including, epistaxis	20 to 40% Dose 10 to 20 (±5) IU/kg	Repeat infusions every 12 to 24 h. Duration: at least 1 day, until the bleeding episode is resolved or healing is achieved
Moderate Moderate bleeding into muscles, bleeding into the oral cavity, definite/more extensive hemarthroses, and known trauma	30 to 60% Dose 15 to 30 (±5) IU/kg	Repeat infusions every 12 to 24 h for 3 days or more until the pain and acute disability/incapacity are resolved
Major Significant gastrointestinal bleeding, intracranial, intra-abdominal, or intrathoracic bleeding, central nervous system bleeding, bleeding in the retropharyngeal or retroperitoneal spaces or iliopsoas sheath, fractures, head trauma	60 to 100% Dose 30 to 60 (±5) IU/kg In case of life-threatening bleeds, a dose of 80 (±5) IU/kg may be considered	Repeat infusions every 8 to 12 h until the bleeding episode/threat is resolved

The required units will be calculated according to the following formula:

$$\text{body weight (kg)} \times \text{desired FVIII rise (\%)} \text{ (IU/dL)} \times \{\text{reciprocal of observed recovery}\}$$

Whenever possible, the subject's most recent individual IR should be used. In its absence, an anticipated recovery of 2.5 (IU/dL)/(IU/kg) based on data of the Phase 1 study, Cohort 2, should be assumed and the required units calculated using the following formula:

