20.2.2.3 Baseline Visit / Start of Prophylaxis

This visit takes place 6 ± 1 weeks following the PK assessment, or following screening if a PK was already available in case of transitioning subjects. This visit will then coincide with confirmation of eligibility. It is the baseline time point for all subsequent visits.

At least 84 to preferably 96 hours must have elapsed since the previous BAX 855 administration and at least 72 hours since the previous administration of any other FVIII concentrate in case of BAX855 naïve subjects, and the subject must not be actively bleeding.

The following procedures will be performed:

Pre-infusion:

- Confirmation of eligibility for transitioning subjects with previous PK data
- Physical examination, including height (for subjects aged < 18 years at enrollment) and body weight
- Review and discuss subject e-diary, including:
 - Review bleeding episodes and their treatment (not applicable for BAX855 naïve subjects)
 - Adverse events
 - Concomitant medications and non-drug therapies
- Laboratory assessments within 30 minutes of start of infusion:
 - FVIII activity and antigen
 - TGA parameters and VWF antigen (optional in subjects aged <12 years)
 - Immunogenicity tests
 - Hematology, clinical chemistry, and lipid panel
- PROs:
 - Bleed and pain severity using Haemo-SYM (≥ 18 years), HRQoL using SF-36 (≥ 14 years), HRQoL using PedsQL (< 14 years), patient satisfaction with treatment using the Satisfaction Questionnaire (all ages), and Patient Activity Level (all ages)
- Vital signs (within 15 minutes of start of infusion)

Determination of IR:

- Infusion of 60 ± 5 IU/kg BAX 855

Post-infusion:

At 30 ± 15 min post-infusion:

- FVIII activity and antigen
- TGA parameters (optional in subjects aged < 12 years)
- Vital signs

Other procedures:

- Dispense IP:
 - A sufficient quantity of IP will be dispensed to cover the period until the next scheduled visit in 4 ± 1 week.

20.2.2.4 Follow-up Visits: At 4 (\pm 1) Weeks, 8 (\pm 1) Weeks, 18 (\pm 2) Weeks from Baseline Visit

No wash-out period is required for this visit and the patient should not be in a bleeding state.

The visit should be performed immediately prior to the next regular prophylactic infusion in order to determine adequate FVIII trough levels.

The following assessments will be performed:

Pre-infusion:

- Physical examination, including height (for subjects aged < 18 years at enrollment) and body weight
- Review and discuss subject e-diary, including:

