- ^a The screening visit procedures, including laboratory evaluations, are to be completed within 45 days prior to the infusion of BAX 855 at the PK assessment. The procedures/assessments marked with an asterisk (*) will be transcribed from the end of study visit of the previous BAX 855 study for transitioning subjects. However, the following assessments are not part of the end of study assessments of the previous BAX 855 study and must be performed at screening to ensure eligibility: Performance score (Karnofsky or Lansky), viral serology (see Section 20.4.3), and pregnancy test if female of childbearing potential. Additionally, for subjects transitioning from the surgery study (Study 261204), FVIII assays and lipid panel (see Section 20.4.3) should also be performed. **Note:** Subjects can decide at any time during the continuation study to receive a PK-tailored dosing regimen. For this purpose, all the study visits starting from the PK assessment, if needed, will apply, however, the screening visit is not applicable.
- ^b PK assessment does not need to be performed in transitioning subjects who have already undergone a PK assessment in a previous BAX 855 study. For these subjects the baseline/start of prophylaxis visit will be the first visit after the screening visit and eligibility will be confirmed at this visit.
- ^c Baseline/start of PK-tailored prophylaxis starts 6±1 week following either PK determination in case the patient has not undergone a PK in a previous BAX855 study or 6±1 week following screening if a PK is already available. This visit will then coincide with confirmation of eligibility.
- ^d Including cases of withdrawal or discontinuation.
- ^e Occurs at enrollment at latest (prior to any study-specific procedure). For transitioning subjects from other BAX 855 studies, to give the patient sufficient time to review the ICF, this document should preferably be provided prior to the end of study visit of the previous study.
- ^f Medical history to include hemophilia history (confirmation of diagnosis & severity; family history of hemophilia; documentation of a mutation, if known; and presence of any target joints).
- ^g Medication history to include documentation of all FVIII replacement therapies used within the last year, any prior history of use of any PEGylated medication (eg, PEG-interferon) at any time in the past, and other medications in the last 30 days.

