#### 6. STUDY SUBJECTS

## 6.1 Disposition of Subjects

All subjects with informed consent provided are to be accounted for in this study.

Each subject is to participate in the study until a total of at least 100 EDs to BAX 855 have been achieved (accumulated across all BAX 855 studies in which each subject participated in).

Depending on the subject's BAX 855 exposure history and treatment regimen given, the planned duration of subject participation to reach the 100 EDs vary from approximately three to 12 months.

The following information is to be obtained from the eCRF:

- Informed consent (*Informed Consent* eCRF panels).
- Protocol version the subject enrolls onto the study (*Protocol Version* eCRF panels).
- Inclusion and exclusion criteria met and/or not met (*Inclusion/Exclusion Criteria* eCRF panels).
- Visit dates (*Date of Visit* eCRF panels).
- Other studies in the BAX 855 program the subject participated in (*Demographics* eCRF panels).
- Study completion (*Completion/Termination* eCRF panels):
- AE term and number (*Adverse Event* eCRF panels).
- Transfer to surgery study (if applicable; *Transfer to Surgery Study* eCRF panels).

- Return from surgery study (if applicable; *Return from Surgery Study* eCRF panels).
- Treatment regimen including date of treatment regimen start (*Treatment Regimen* and *Change in Treatment Regimen* eCRF panels).
- BAX 855 administration (*Study Infusions* eCRF panels).

The following derivations based on eCRF reported results are to be performed:

- A subject is considered to be enrolled if date of informed consent is present.
- A subject is to be assigned as dosed with a particular treatment regimen if the subject received any BAX 855 infusion when assigned to the particular regimen.
   Treatment regimen assignments are described in Section 5.11: Examination of Subgroups.
- A subject is considered to be completed if the reason for termination indicates the subject completed the study. Otherwise the subject is to be considered discontinued.

Planned presentation of tables on the disposition of subjects are to include a summary of disposition and analysis sets on the ENR set.

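### SAP 6.8 reports dose adherence by regimen but divides by all of the subject's infusions, so a perfectly dosed subject who changes regimen scores below 100% in each regimen, and bleed infusions usually lower the figure too

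*SAP*

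**What the plan says.** SAP 6.8 calls an infusion dose-adherent if the amount given lies between 90% and 110% of the planned IU/kg. The number and percentage of such infusions are found per subject and treatment regimen, "using the overall number of infusions for that subject as denominator". The only stated exclusion is infusions with no recorded amount. On reporting, SAP 6.8 says: "Summaries are to be presented by age category and treatment regimen at time of dose on a subject level". The tables are produced for the safety and per-protocol sets.

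SAP 6.8 builds on SAP 6.7, where infusions are counted "overall and by reason for infusion as well as by the treatment regimen assigned to at the time of receiving the treatment". SAP 6.1 treats a subject as dosed with a regimen "if the subject received any BAX 855 infusion when assigned to the particular regimen", so a switcher belongs to more than one.

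The protocol provides for regimen changes:
- Former on-demand subjects of the pivotal study who "decide to receive a PK-tailored treatment regimen in this study will first receive a fixed dose prophylactic treatment regimen" (Protocol 8.7.3).
- For PK-tailored subjects the baseline visit falls 6 ± 1 "weeks following the PK assessment, or following screening if a PK was already available" (Protocol 20.2.2.3).
- "Subjects can decide at any time during the continuation study to receive a PK-tailored dosing regimen" (footnote a to the PK-tailored schedule, Protocol 20.3.3).

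Bleeds are treated under Protocol Table 3. A moderate bleed, for example, has "Dose 15 to 30 (±5) IU/kg", repeated every 12 to 24 hours for at least 3 days. SAP 7.1 takes bleed-treatment and prophylactic infusions from the same Study Infusion panels.

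**The concern.** The percentage is meant to show how closely subjects kept to their planned prophylactic dose under each regimen. As written, it also depends on two things unrelated to that.

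- **Regimen mix.** The numerator counts infusions on one regimen and the denominator counts infusions on all of them. A table by regimen would then show a change of regimen as poor dosing.
- **Treated bleeds.** An infusion given for a bleed has its own dose guidance, but it stays in a denominator meant for prophylaxis.

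At stake are the dose-adherence tables and possibly one of the prompts for per-protocol review. SAP 4.4 lists being less than 75% compliant with the planned dosing regimen as a point for the analysis-set meeting. It does not say which percentage is meant. If it is this one, subjects who bleed more are more likely to be raised.

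**Working it through.** The SAP states no compliance figure, so there is none to reproduce. The check applies the written rule to a subject whose every prophylactic dose is inside the band, for whom the right answer is 100%.

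**Meaning of the denominator.** SAP 6.7 lists the overall count beside the by-reason and by-regimen counts, so the overall count is the unsplit one. SAP 7.1 divides bleeds by the observation time for the particular regimen when it derives ABR, so the SAP does write a regimen-matched denominator where it wants one.

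**Control.** No regimen change and no bleed: 100/100 = 100%. The rule works here.

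**1. Regimen change**

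Score for regimen r = adherent infusions on r ÷ all infusions of the subject. With perfect dosing this is the share of infusions given on r.

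Assumptions: a twice-weekly lead-in of 6 weeks (6 × 2 = 12 infusions; 10 to 14 for 5 to 7 weeks), recorded as its own regimen; then twice-weekly PK-tailored dosing for 3 months (26 infusions) or 12 months (104).

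| Lead-in + PK-tailored | Fixed-dose score | PK-tailored score |
|---|---|---|
| 12 + 26 | 12/38 = 31.6% | 26/38 = 68.4% |
| 10 + 26 | 10/36 = 27.8% | 26/36 = 72.2% |
| 14 + 26 | 14/40 = 35.0% | 26/40 = 65.0% |
| 12 + 104 | 12/116 = 10.3% | 104/116 = 89.7% |

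Each pair sums to 100%, so one of two regimens always scores 50% or lower.

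The documents give no number of switchers. If a share s of the PK-tailored column had the 12 + 26 pattern and everyone else scored 100%, the column mean would be 100 − 31.6s: 96.8%, 92.1% and 84.2% for s = 0.10, 0.25 and 0.50. These shares are illustrations only.

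**2. Bleed infusions**

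- Lowest planned fixed twice-weekly dose (Protocol 8.7.3.1): 45 − 5 = 40 and 50 − 10 = 40 IU/kg. Lower adherence limit: 0.9 × 40 = 36 IU/kg.
- Table 3 maxima before vial rounding: minor 20 + 5 = 25 IU/kg; moderate 30 + 5 = 35 IU/kg. Both are below 36, so such infusions count as non-adherent.
- One moderate bleed over 3 days: 3 infusions at 24-hour intervals, 6 at 12-hour intervals.
- With 26 prophylactic infusions: 26/29 = 89.7% to 26/32 = 81.3%. With 104: 104/107 = 97.2% to 104/110 = 94.5%.
- Falling below 75% takes 9 out-of-band infusions in 3 months (26/34 = 76.5%; 26/35 = 74.3%) or 35 in 12 months (104/138 = 75.4%; 104/139 = 74.8%).

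Some bleed infusions land inside the band:
- *Vial rounding* (allowed for bleed doses, Protocol 8.7.2). At 70 kg and 30 IU/kg the dose is 2,100 IU; rounded up with 1,000 IU vials it is 3,000 IU, and 3,000/70 = 42.9 IU/kg. The band for a planned 45 IU/kg is 40.5 to 49.5.
- *Major bleeds.* Table 3 spans 30 − 5 = 25 to 60 + 5 = 65 IU/kg, which overlaps that band.
- *Lower planned doses.* At 30 IU/kg (possible on the every 5 or 7 day regimens) the band is 27 to 33, which overlaps the moderate range of 10 to 35.

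Such an infusion would be counted as an adherent prophylactic dose, which is also wrong.

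**After the fix.** The 12 + 26 subject scores 12/12 and 26/26, that is 100% in each regimen, however many bleeds are treated.

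**The case against.** The strongest reply is that this is a descriptive table with little resting on it. The 75% exposure prompt in SAP 4.4 points to Section 6.8, but the 75% dosing prompt has no such pointer. The prompts lead to a discussion attended by Biostatistics and Medical, not to automatic exclusion. All of that stands and limits the importance of the point.

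The size of the switcher effect can also be questioned. The example needs the lead-in to be recorded as a regimen of its own, which the documents do not confirm. BAX 855 naïve subjects have no such lead-in, because they stay on their own FVIII product until baseline apart from one PK infusion (Protocol 10.3.2). The group expressly required to start on fixed dosing comes from 17 planned on-demand subjects in the pivotal study (Protocol 6.1). This limits how many subjects are affected. It does not repair the rule, since a change to PK-tailored dosing is open to any subject at any time.

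A reader might infer more than the documents support:
- *That every compliance figure falls as bleeds are treated.* It does not. Schedule adherence and Time Exposed (%) depend on the time since the last infusion of any kind, and an extra infusion shortens that gap. Only the dose-adherence percentage can fall.
- *That every bleed infusion counts as non-adherent.* The in-band cases above show otherwise.
- *That recovery, PK and surgery infusions also inflate the denominator.* This is not shown. SAP 4.2 lists separate eCRF panels for them, and SAP 6.7 draws on the Study Infusions panels.

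**Conclusion.** The denominator error stands, and no other section corrects it. Its regimen-change part follows directly from the text: each regimen's score is capped at that regimen's share of the subject's infusions. The 31.6% and 68.4% rest on the assumed 12 and 26 infusions and on separate recording of the lead-in. Summed over regimens, a perfectly dosed switcher without bleeds still totals 100%, so a reader should not infer that switching lowers a whole-subject figure.

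The bleed part is a usual effect, not a universal one. It lowers the dose-adherence percentage when the bleed dose falls outside the band and flatters it when the dose falls inside.

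The consequence is confined to the descriptive dose-adherence tables on the safety and per-protocol sets and, only if SAP 4.4 uses this percentage, to which subjects come up for per-protocol discussion. It would be wrong to infer a bias in the FAS analysis of the co-primary ABR, since dose adherence does not enter it. The change is worth making because the stated rule gives a wrong number and is easily corrected, not because a main conclusion depends on it.

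**What to change.** Amend SAP 6.8 as follows:
- **By regimen:** count in both numerator and denominator only the subject's prophylactic infusions with a recorded amount given while on that regimen.
- **Whole subject:** use all of the subject's prophylactic infusions with a recorded amount.
- State that infusions to treat bleeds or to maintain hemostasis are left out of both.

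As a small clarification in SAP 4.4, name the percentage that the 75% dosing prompt uses and say that it is applied per subject.

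The cost is SAP wording and programming. No new data are needed, because SAP 6.7 already derives infusion counts by reason and by regimen.
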